Available small studies, case reports (14-22), and our preliminary data (87) support that DDN likely produces neural plasticity at both spinal and supraspinal levels. Thus, our central hypothesis is that ***DDN at MTrP induces plasticity in the spinal and supraspinal pathways and produces therapeutic effects.*** While the steady increase in therapeutic use of DDN implies its clinical potential, its optimal use is yet to be established, largely due to the limited mechanistic understanding of its neurophysiological effects. This pilot project is our first step towards understanding the neurophysiological mechanisms of DDN, specifically the spinal mechanisms of DDN-induced plasticity. This project evaluates these mechanisms via two specific aims:

Aim 1. To evaluate the effects of DDN on proprioceptive reflexes in people with spasticity due to stroke.

In people with spasticity the excitability of the H-reflex pathway (an electrical analog of spinal stretch reflex) becomes elevated and reciprocal inhibition of the plantarflexors by the dorsiflexors becomes impaired (25, 26). Thus, to investigate the effects of DDN at the medial gastrocnemius (MG) MTrP on excitatory and inhibitory proprioceptive reflexes, in 20 individuals with spasticity due to stroke we will measure the H-reflex – M-wave (H/M) recruitment curves and reciprocal inhibition in the triceps surae muscles before, immediately after, 90 minutes after, 24 hours after, and 72 hours after DDN. One week prior to DDN, the same measurements will be repeated 5 times, with inter-measurement intervals matching to pre and post DDN measurements. We anticipate that decreases in H-reflex size and reciprocal inhibition will occur between pre and post DDN time points.

Aim 2. To evaluate the effects of DDN on cutaneous reflexes in people with spasticity due to stroke. Modulation of cutaneous reflexes to non-noxious stimulation of the skin become abnormal

post-stroke, reflecting the altered somatosensory processing in this population (33, 34). Thus, in this project, we will examine cutaneous reflex responses to non-noxious stimulation of the distal limb (i.e., at or below the area treated with dry-needling) at the same time points as the proprioceptive reflexes before and after a single DDN session. We anticipate that cutaneous reflex amplitudes will be decreased after DDN.

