Additionally, to interpret these reflex changes related to typical clinical measures, we will measure passive and active dorsiflexion range of motion (ROM) and the Modified Ashworth scale, Fugl-Meyer, and 10-m walk test. These measurements will facilitate the development of future DDN clinical trials towards establishing spinal neurophysiological mechanisms of DDN.

The findings from this project would also help clinicians estimate when post DDN motor practice/training therapies should be administered for improving motor function in persons with and without spasticity. The data obtained through this pilot project will significantly strengthen our future NIH R-series applications, through which we plan to test the hypothesis that a single administration of DDN procedures will produce lasting effects on spinal neurophysiology that support temporary relief/alleviation of sensorimotor impairments in people with spasticity due to chronic stroke.

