9.0 Study Design / Methods

This study is a partial cross-over waitlist control design, in which each of the 20 participants post stroke will participate in 7 visits over a two-week period, during which measurements will be taken 10 times. Neurophysiological and functional measurements will be collected five times over 3 visits during the first week (treatment as usual control week), through which each participant will serve as their own "controls" for their second week of measurements. No sham or other treatment procedure will occur during this week. On the second week, all participants will transition to the DDN intervention week where five measurements will be collected over 3 visits (one pre-DDN baseline and four post-DDN measurements: immediately after, 90 minutes, 24 hours, and 72 hours).

Deep Dry Needling (DDN)

DDN procedures used in this project have been widely used in clinical practice to treat spasticity and pain in individuals with neurological and non-neurological (orthopedic) injuries [15,16,18,20,21,48,75].

Each participant receives a single session of DDN, targeting the medial gastrocnemius. In each DDN session, first, localized hypersensitive spots in palpable taut bands of the targeted skeletal muscles (i.e., MTrPs)(75, 76) are identified with pincer palpation. Then, after cleaning the skin area over a MTrPs with alcohol swabs, a disposable stainless steel acupuncture needle is inserted into the skin, penetrating approximately 15 to 20 mm to the depth of the trigger point, until the local twitch response (LTR) is elicited. Once the LTR is confirmed, the needle is moved up and down

(~4-5 mm vertically) with a small piston motions (approximately at 1 Hz for 25 to 30 seconds) with no rotation at the MTrPs (9,10, 38). The same procedure is repeated at other MTrPs in the same local skin region as needed until the LTR is eradicated. After removing the needle, the needled area is rubbed to prevent bleeding and bruising. Each participant will complete 5 repetitions of each of the following: ankle plantarflexion/dorsiflexion passive range of motion (PROM), sub-maximal concentric and eccentric contractions of the plantarflexors as would be typical in a clinical setting.

Electromyography (EMG) and nerve stimulation

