At the beginning of each session, surface self-adhesive Ag-AgCl electrodes are placed over the TA, medial and lateral gastrocnemius (MG and LG), and soleus muscles of the studied leg. Throughout the study, all EMG activity is amplified, band-pass filtered (10-1000 Hz), sampled at 3,200 Hz, and stored. Nerve stimulation protocol consists of 4 components: (1) single pulse posterior tibial nerve stimulation for the triceps surae H-reflex / M-wave (H/M) recruitment curve measurement, (2) single pulse common peroneal (CP) nerve stimulation for the TA H/M recruitment curve measurement, (3) multiple pulse (train) tibial nerve stimulation for cutaneous reflex measurement, and (4) multiple pulse (train) superficial peroneal (SP) nerve stimulation for cutaneous reflex measurement.

- (1) ***Single pulse posterior tibial nerve stimulation for triceps surae H/M recruitment curve:*** To elicit the triceps H-reflex, the tibial nerve is stimulated in the popliteal fossa, using surface Ag-AgCl electrodes and isolated constant current stimulation. The stimulating electrode pair is placed so as to minimize the H-reflex threshold and to avoid stimulation of other nerves. For eliciting the H-reflex and M-wave, a 1-ms square stimulus pulse is delivered when the participant has maintained his/her natural standing level (typically, 10-20% of maximum voluntary contraction (MVC) level of EMG activity) of soleus EMG activity for at least 2 s. The minimum interstimulus interval is 5 s. An H/M recruitment curve is obtained by gradually increasing the stimulus intensity in increments of 1.2-2.5 mA from the H-reflex threshold to the maximum H-reflex (H_{max}) to an intensity just above what is needed to elicit the maximum M-wave (M_{max}) [77-79], while the participant stands and maintains the above noted level of soleus EMG activity. About 10 different intensities are used to obtain a recruitment curve, and four EMG responses are averaged to measure the H-reflex and M-wave at each intensity. Then, about 100 responses are elicited at the H_{max} level of stimulus intensity (i.e., weak to mild intensity) while monitoring cortical electroencephalographic (EEG) activity.

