- (2) ***Single pulse common peroneal (CP) nerve stimulation for TA H/M recruitment curve:*** To elicit the H-reflex and M-wave in the TA, the CP nerve is stimulated at the neck of the fibula, using surface Ag-AgCl electrodes and isolated constant current stimulation. For eliciting the H-reflex and M-wave, a 0.5-ms square stimulus pulse is delivered when the participant has maintained his/her natural standing level of soleus EMG activity for at least 2 s, with the minimum interstimulus interval of 5 s. An H/M recruitment curve is obtained by gradually increasing the stimulus intensity from the H-reflex threshold to the H_{max} to an intensity just above what is needed to elicit the M_{max} [77-79], while the participant stands and maintains the above noted level of soleus EMG activity. About 10 different intensities are used to obtain a recruitment curve, and four EMG responses are averaged to measure the H-reflex and M-wave at each intensity. Then, about 100 responses are elicited at the H_{max} level of stimulus intensity (i.e., weak to mild intensity) while monitoring cortical EEG activity.
- (3) ***Train of tibial nerve stimulation for cutaneous reflexes:*** The distal tibial nerve is stimulated on the medial surface of the ankle posterior to the medial malleolus by trains of five pulses at 200 Hz, with a pulse width of 1.0 ms [34,80]. The stimulus electrodes are placed at a location at which strong radiating paresthesia is reported by the participant in the appropriate cutaneous

receptive fields (i.e., plantar surface of foot). While standing, the perceptual threshold, defined as the lowest stimulation detectable by the participant, and the radiating threshold (RT), defined as a clear radiating paresthesia, are determined. Perceptual threshold is thought to represent local activation of cutaneous receptors lying immediately underneath the recording electrodes, whereas RT is likely representing electrical activation of fascicles in the underlying cutaneous nerve [80,81]. 1×RT, 2×RT, and 3×RT of train of stimuli are delivered while the standing participant maintains the above described level of soleus EMG activity. Fifteen to 20 trials are averaged for each stimulus intensity, with the minimum inter-train interval of 5s.

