(4) ***Train of superficial peroneal (SP) nerve stimulation for the cutaneous reflexes:*** The SP nerve is stimulated on the anterior surface of the leg just near the crease of the ankle joint by trains of five pulses at 200 Hz, with a pulse width of 1.0 ms [34,80]; the stimulus location at which the participant receives strong radiating paresthesia in the appropriate cutaneous receptive fields (i.e., foot dorsum). While standing, the perceptual threshold and the RT are determined. 1×RT, 2×RT, and 3×RT of train of stimuli are delivered while the standing participant maintains the above described level of soleus EMG activity. Fifteen to 20 trials are averaged for each stimulus intensity, with the minimum inter-train interval of 5s.

Analysis of H-reflex and cutaneous reflexes

The H-reflex and the M-wave amplitudes are measured as the peak-to-peak values in time windows determined for each participant. Typically, for the soleus, the H-reflex occurs in a time window of 30–50 ms post-stimulus 6–25 ms post-stimulus for the M-wave. For the MG, LG, and TA, the M-wave and H-reflex occur with shorter latencies [79]. For all muscles, the H_{max} , M_{max} , and H_{max}/M_{max} ratio are obtained from the recruitment curve measurement.

To analyze cutaneous reflexes, the background (prestimulus) EMG is subtracted from the post-stimulus EMG trace [34,78]. Then, subtracted EMG traces from each muscle are analyzed for peak reflex amplitudes at two distinct epochs termed early (~50–75 ms to peak) and middle (~75–120 ms to peak) latencies [78,83].

Assessment of sensory and motor function

Fugl-Meyer Assessment: Fugl-Meyer Assessment is one of the most widely used quantitative measures of motor impairment and recovery in post-stroke hemiparetic individuals. The assessment includes: motor function (upper extremity maximum score = 66; lower extremity maximum score = 34), sensory function (maximum score = 24), balance (maximum score = 14), joint range of motion (maximum score = 44), and joint pain (maximum score = 44). Each item is scored on a 3-point ordinal scale: 0 = cannot perform, 1 = performs partially, 2 = performs fully. The maximum score is 226.

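### Aim 2 predicts decreased cutaneous reflexes, but the protocol yields 48 cutaneous amplitudes at each time, names no primary among them and specifies no correction across them

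*Combined protocol and SAP*

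**What the plan says.** The Aim 2 prediction in section 1.0 reads "We anticipate that cutaneous reflex amplitudes will be decreased after DDN". It names no muscle, nerve, intensity, epoch or time.

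Section 9.0 sets out what is measured:

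- **Muscles:** electrodes go on the TA and on the "medial and lateral gastrocnemius (MG and LG), and soleus muscles of the studied leg", four muscles in all.
- **Nerves:** cutaneous reflexes are evoked from two nerves, the distal tibial and the superficial peroneal.
- **Intensities:** for each nerve, "1×RT, 2×RT, and 3×RT of train of stimuli are delivered", and trials are averaged within each intensity.
- **Epochs:** "subtracted EMG traces from each muscle are analyzed for peak reflex amplitudes at two distinct epochs", early and middle.
- **Times:** the DDN week has "one pre-DDN baseline and four post-DDN measurements: immediately after, 90 minutes, 24 hours, and 72 hours". For the preceding control week, "Neurophysiological and functional measurements will be collected five times over 3 visits during the first week". Aim 1 describes the control measurements as spaced "with inter-measurement intervals matching to pre and post DDN measurements", and Aim 2 uses the same time points.

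The analysis is in section 10.0. Reflex sizes before and after needling are compared by a two-way repeated measures ANOVA (studied side by time), followed by Bonferroni-corrected t-tests as post-hoc tests. Alpha is not stated. Neither section ranks the cutaneous measures or pools them into a summary.

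**The concern.** One directional prediction can be met by any of 48 amplitudes at any of four post-DDN times. Muscle, nerve, intensity and epoch are not factors in the ANOVA, so the plan as written implies a separate ANOVA for each measure. A Bonferroni step attached to post-hoc tests ordinarily covers the time contrasts within one ANOVA. On that reading, nothing limits the error rate across measures, and a reader of the results could not tell a real decrease from the most favourable of many null ones.

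The use of the results raises the stakes. Section 1.0 says "The data obtained through this pilot project will significantly strengthen our future NIH R-series applications", and also expects the findings to help clinicians judge when to give training after DDN. A chance decrease could set the muscle, nerve, intensity or time point of the next study.

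**Working it through.** The plan gives no error rate, alpha or count of cutaneous measures, so there is no stated figure to reproduce.

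**Count (levels from section 9.0)**

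- 4 muscles × 2 nerves × 3 intensities × 2 epochs = 48 amplitudes per measurement time.
- 48 × 4 post-DDN times = 192 pre/post contrasts in the DDN week.
- If the three intensities are averaged: 4 × 2 × 2 = 16 measures.

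**Chance of at least one false decrease**

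From the plan: 20 participants and 5 DDN-week times. Assumed:

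- two-sided alpha 0.05 and no DDN effect;
- normal data, with all measures equally correlated;
- one repeated measures ANOVA over time for each measure. The side factor is left out because section 9.0 describes electrodes on the studied leg only.

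A false decrease means a significant ANOVA followed by at least one significant fall from the pre-DDN value. Two Bonferroni families were tried: the four pre/post tests (0.05/4 = 0.0125 each) and all ten pairs of the five times (0.05/10 = 0.005 each). Simulation gives:

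| Measures | Bonferroni family | r = 0 | r = 0.5 | r = 0.7 | r = 0.9 |
|---|---|---|---|---|---|
| 48 | 4 pre/post tests | 41% | 22% | 14% | 6% |
| 48 | 10 time pairs | 26% | 15% | 10% | 3% |
| 16 | 4 pre/post tests | 17% | 12% | 8% | 4% |
| 16 | 10 time pairs | 10% | 8% | 5% | 2% |

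Repeat runs differ by about one percentage point. The comparator is one pre-named two-sided test, which gives a false decrease with probability 0.05/2 = 2.5%.

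**Detectable change (paired t-test, n = 20, 80% power)**

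- One test at two-sided 0.05, unadjusted: 0.66 SD of the DDN-week change.
- Adjusted for the control week, with equal variances and correlation r between the two weeks' changes: 0.66 × √(2(1 − r)) = 0.93, 0.81, 0.66 and 0.47 at r = 0, 0.25, 0.5 and 0.75.
- Bonferroni over 48 (0.05/48 = 0.00104): about 1.08 SD.
- Benjamini-Hochberg over the other 192 − 1 = 191 contrasts, for an isolated true effect (p near 0.05/191 = 0.00026): about 1.22 SD of the control-adjusted change.

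**The case against.** The strongest reply is that this is a pilot. Section 1.0 calls it a first step, section 2.0 gives the goal as characterising effects, and the hypothesis test is placed in later grant-funded work. Reporting several muscles, nerves and intensities suits that purpose, and labelling the cutaneous results exploratory would answer most of the concern. This stands as a limit on severity. It does not remove the point, because the plan pairs a directional prediction with formal tests and carries no such label.

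A reader might infer three stronger claims, and the documents do not support them.

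- **An error rate of 70% for a false decrease, or 91% for a change in either direction.** These are 1 − 0.975^48 = 0.703 and 1 − 0.95^48 = 0.915. They need 48 independent measures, which is unlikely in the same participants, and they skip the planned ANOVA and Bonferroni steps.
- **That the Bonferroni correction definitely leaves the 48 measures uncorrected.** Section 10.0 does not define the family. The firm statement is that no correction across the 48 is specified.
- **That a decrease is undefined for a response below background.** Section 9.0 gives no sign rule for the background-subtracted peak, but it cites sources for the method that may supply one. This supports only a request to state the convention.

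It is also fair that nothing says each intensity is tested separately, which is why the 16-measure rows are shown. The use of the control week is a different issue from multiplicity and is kept separate in the fix.

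**Conclusion.** The point holds. Aim 2 has 48 candidate amplitudes, no primary and no specified correction across them. Under the stated assumptions, the chance of at least one false decrease with 48 measures runs from about 41% down to 3%, depending on correlation and Bonferroni family. With 16 measures it runs from about 17% to 2%. Most of these exceed 2.5%; at correlation 0.9 with ten time pairs the excess all but disappears.

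Alpha, the correlations, the Bonferroni family and the omission of the side factor are all assumptions, so no single figure is the error rate of the written plan. The gap itself is certain and its size is not. In a pilot it should be fixed before analysis, but it does not invalidate the study. The likely harm is over-reading a chance result when planning the next one.

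**What to change.** Before analysis, make three changes to section 10.0.

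1. **Name one primary measure for Aim 2.** Suggested text:

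   > The Aim 2 primary measure is the [early or middle] latency response of [one muscle] to stimulation of [one nerve], at [one intensity, or the mean of the three], at [one post-DDN time], tested at two-sided 0.05. All other cutaneous measures and times are exploratory and are reported with estimates and confidence intervals. If p-values are used to claim effects among them, the Benjamini-Hochberg procedure at 5% is applied across them.

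   The investigators choose the measure.

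2. **Separately, use the control week.** Test (DDN-week post minus pre) minus (control-week change over the matched interval). Section 9.0 makes participants their own controls, but the ANOVA in section 10.0 names no week factor. As an illustration, a downward drift of 0.3 SD shared by both weeks gives a false decrease in 25% of unadjusted tests and 2.5% of adjusted ones.

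3. **State the sign convention.** Say whether the background-subtracted peak is signed or absolute, and what counts as a decrease in a suppressive response.

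This takes a few sentences and no new data or visits. The costs are:

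- The investigators must commit to one measure with little prior data.
- The control-adjusted test is less sensitive than the unadjusted one if the two weeks' changes correlate below 0.5, and more sensitive above that.
- An isolated exploratory effect is hard to claim under false-discovery control (about 1.22 SD), so most exploratory results will rest on estimates and intervals.
- Aim 1 is unchanged by this text, so the two aims would be analysed differently unless the investigators align them.

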10.0 Data Management

Data analysis: Reflex sizes are calculated in reference to each participant's M_{max} measured during natural standing. For example, the peak-to-peak H-reflex amplitude is normalized to the peak-to-peak M_{max} amplitude, and the mean rectified H-reflex amplitude is normalized to the mean rectified M_{max} amplitude.

For comparing reflex sizes before and after dry needling, a two-way repeated measures ANOVA (studied side of the extremity \times time) will be used, together with Student t-test with Bonferroni correction as a post-hoc test. For simple comparison between participants without known neurological conditions and participants after stroke (e.g., age and M_{max}), and assessments of changes in sensory and motor function (i.e., only applicable to participants after stroke), a Student t-test will be used.

Data management: The data will be managed by the PIs and research coordinator at the College of Health Professions (CHP). All EMG and assessment data are electronically stored in the secure CHP server with password protection. Only the investigators directly involved in this project have access to these data.

Protection of participant confidentiality is essential in human clinical trials. The participants' confidential information will be securely stored in locked cabinets of a locked room and a password-protected computer, and only the principal and co-investigators and the research coordinator will have access to the participant's confidential information. For the length of the study, limited personal information (specifically, the participant's name, address, and social security number) will also be accessible to the program administrator for processing the participant reimbursement paperwork. Investigators and therapists, who run data collection sessions, will have access to the EMG and other collected data for the purpose of analysis, but will have no access to the participant's confidential information. Alphanumeric codes will be assigned to each participant's dataset to protect confidentiality.

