5.0 Number of Subjects

Twenty adults (≥ 18 years old) with spastic hyperreflexia due to stroke are recruited from the community around the MUSC and a greater Charleston area.

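### The reflex analysis (studied side by time) never compares needling-week change with control-week change, so the planned control week does not serve as a control

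*Combined protocol and SAP*

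**What the plan says.** Section 1.0 (Aim 1) sets up the control: "One week prior to DDN, the same measurements will be repeated 5 times, with inter-measurement intervals matching to pre and post DDN measurements". Section 9.0 repeats it: "Neurophysiological and functional measurements will be collected five times over 3 visits during the first week (treatment as usual control week"), and says that participants act as their own controls for the second week. Of that first week it adds: "No sham or other treatment procedure will occur during this week". The second week has one pre-DDN and four post-DDN measurements (immediately, 90 minutes, 24 hours, 72 hours). In all there are 10 measurements, five per week.

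The only analysis text is the data analysis paragraph of section 10.0. For reflexes it says "For comparing reflex sizes before and after dry needling, a two-way repeated measures ANOVA (studied side of the extremity" by time), with Bonferroni-corrected Student t-tests post hoc. It does not define the levels of side or time, or list the post-hoc comparisons. Changes in sensory and motor function get a Student t-test, with no mention of the control week. The paragraph also contains this: "For simple comparison between participants without known neurological conditions and participants after stroke".

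**The concern.** The study has no sham, no parallel group and no randomised order. The untreated week is its only control, and it takes half of the measurements. To use it, the analysis must ask whether the change from the first to the later measurements is larger in the DDN week than in the control week. Section 10.0 does not ask that.

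Change within a week without needling is plausible. Each measurement includes recruitment curves for two nerves, about 100 further responses at the Hmax intensity for each, and cutaneous stimulus trains at three intensities for two more sites. Three such measurements fall around the needling session (before, immediately after, at 90 minutes). If responses shift with repeated testing, an analysis of the DDN week alone attributes the shift to DDN. Section 1.0 says the data are to support later grant applications, so a false signal would carry into their planning.

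**Working it through.** **1. Can the written analysis be read so that it uses the control week?**

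- *Time has five levels (the DDN week).* This fits the stated purpose of comparing before with after needling. The control week is then absent.
- *Time has all 10 levels.* Control-week data enter the model, and there are 10 × 9 / 2 = 45 pairwise tests. Each compares two occasions. The contrast needed involves four occasion means:

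  (post − pre in the DDN week) − (post − pre in the control week).

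  None of the 45 pairs is that contrast.
- *Side acts as the control.* Section 9.0 places recording electrodes on the tibialis anterior, gastrocnemii and "soleus muscles of the studied leg", and describes no second leg. Side then appears to have one level. If both legs were recorded, side by time would compare legs, and the weeks would still not be compared.
- *The wording is shorthand for the intended comparison.* The same paragraph plans a comparison with people without neurological conditions, yet section 5.0 says "Twenty adults (≥ 18 years old) with spastic hyperreflexia due to stroke are recruited" and no other group is enrolled. The paragraph does not fit this design, so an unstated control comparison cannot be presumed.

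**2. Size.** The plan gives no alpha, power, SD or drift, so there is no figure of its own to reproduce. Inputs: n = 20 (section 5.0) and four post times (section 9.0). Assumed: two-sided family alpha 0.05, so 0.05 / 4 = 0.0125 per test; independent normal residuals scaled so that the SD of a post-minus-pre change is 1; no DDN effect; drift equal at all four post times and in both weeks. Simulated percentage of trials with a significant result (40,000 trials; 20,000 for the omnibus tests):

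| Test | Drift 0 | 0.3 | 0.5 | 0.75 |
|---|---|---|---|---|
| Any of four post-vs-pre tests in the DDN week, 0.0125 | 4.2 | 27.8 | 63.7 | 94.4 |
| Time effect in the DDN week, 0.05 | 5.1 | 22.5 | 57.7 | 93.0 |
| Post-vs-pre pairs in the DDN week, 0.05 / 45 | 0.5 | 5.7 | 26.3 | 68.4 |
| Any of four control-adjusted contrasts, 0.0125 | 4.6 | 4.4 | 4.3 | 4.3 |
| Week by time interaction, 0.05 | 5.2 | 5.0 | 4.9 | 4.7 |

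An independent rerun of the simulation agreed to within about one percentage point.

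**3. Unequal drift.** Drift in units of SD; any of four tests at 0.0125:

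| Control week | DDN week | DDN-week tests only | Control-adjusted contrasts |
|---|---|---|---|
| 0.5 | 0.25 | about 20% | 12% |
| 0.75 | 0.25 | about 20% | 37% |
| 0.5 | 0 | about 4% | 36% |
| 0.75 | 0 | about 4% | 69% |

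**4. Power cost.** The SD of the control-adjusted contrast is √(2(1 − ρ)) times the SD of one week's change, where ρ is the correlation between the two weeks' changes. For a paired t-test with n = 20, the noncentral t gives an effect detectable with 80% power of 0.81 SD at alpha 0.0125 and 0.66 SD at 0.05.

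- ρ = 0: multiplier √2 = 1.414, giving 1.15 SD (0.0125) and 0.93 SD (0.05).
- ρ = 0.3: multiplier 1.183, giving 0.96 and 0.78 SD.
- ρ = 0.5: multiplier 1, giving 0.81 and 0.66 SD.
- ρ = 0.7: multiplier 0.775, giving 0.63 and 0.51 SD.

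**The case against.** Time is undefined, and if it covers all 10 occasions the control-week data do enter the model. Its pairs would then flag common drift in the control week about as often as in the DDN week, and an attentive reader might see it. That is fair, and it means misreading is not certain under this version. But setting two sets of significance results side by side is not a test of their difference, and no such test is planned.

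The adjustment is also not uniformly protective. If testing effects wear off after the first week, subtracting the control-week change adds bias: with drift of 0.75 then 0.25 SD the adjusted contrasts err more often than the DDN-week tests alone (37% against about 20%), and with drift in the first week only the gap is wider. This stands as a limit of the fixed week order. It is a reason to state the assumption, not to leave the only control out of the test.

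Two smaller points also stand. Drift is assumed, and its direction matters: the protocol expects decreases, so upward drift would hide an effect and not imitate one. And the power loss is real if the two weeks' changes are weakly correlated; the documents say nothing about ρ. That this is a pilot, with an aim worded as pre versus post, does not remove the mismatch with the design the protocol describes.

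**Conclusion.** The concern holds and should be corrected before analysis. That no week factor or difference-in-change contrast is specified follows from the text alone, with high confidence, and no reading of time or side supplies one.

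The size of the harm is conditional. The rise from roughly 4% to 28–94% false findings depends on drift of 0.3–0.75 SD, taken as equal across post times and independent of treatment. With no drift the plan's tests keep their nominal error. The advantage of the adjusted contrast depends on drift being similar in the two weeks.

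**What to change.** In section 10.0, replace the side by time model with week (control, DDN) by time (pre, immediate, 90 minutes, 24 hours, 72 hours), as a repeated-measures ANOVA or an equivalent mixed model.

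- Name the week by time interaction as the test of DDN.
- List four Bonferroni-adjusted post-hoc contrasts, one per post time: change from pre in the DDN week minus the matched change in the control week.
- Compare change in the functional outcomes between weeks in the same way, with a method suited to ordinal data for the Modified Ashworth Scale.
- State whether one or both legs are recorded; if both, define side as a further factor.
- State that the contrast removes only drift common to both weeks. It does not remove effects of the fixed week order or of having no sham. Reporting each week's change beside the contrast would let readers judge this.
- Separately, remove or reconcile the comparison with participants without neurological conditions. This is a wording mismatch and does not bias the DDN estimate.

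The cost is analysis wording only; all the data are already planned. The statistical price is a detectable effect of up to 1.15 SD in place of 0.81 SD at alpha 0.0125 if the weekly changes are independent, and no loss if they correlate at 0.5.
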